### **Study Intervention(s)**

GWP42003-P solution (100 mg/mL CBD in sesame oil with anhydrous ethanol (10% v/v), sweetener [sucralose], and strawberry flavoring).

Placebo solution (sesame oil) containing the excipients anhydrous ethanol (10% v/v), sweetener (sucralose), strawberry flavoring, and beta carotene.

#### **Part A:**

Participants will initiate IMP at a dose of 2.5 mg/kg BID (5 mg/kg/day morning and evening), and after 1 week, the dose will be increased to 5 mg/kg BID (10 mg/kg/day) as per randomization. Participants may then remain at this maintenance dose for 13 weeks.

For participants who are tolerating IMP at 10 mg/kg/day and require further reduction of seizures, dose escalation up to a maximum daily dosage of 20 mg/kg/day (in increments of 5 mg/kg/day [2.5 mg/kg BID] no more rapidly than every 7 days) may occur after Day 15 based on the investigator's assessment of safety and tolerability. If a dose becomes poorly tolerated in the investigator's opinion, the investigator may consider reducing the dose.

#### **Part B:**

Participants not entering Part B or who discontinue IMP early will down-titrate over a period of 10 days. Participants eligible to enter Part B will enter the blinded transition period. Part B GWP42003-P will be titrated to 10 mg/kg/day whilst blinded IMP is simultaneously tapered down to zero. For participants who are tolerating IMP at 10 mg/kg/day and require further reduction of seizures, dose escalation up to a maximum daily dosage of 20 mg/kg/day may occur after Day 15 based on the investigator's assessment of safety and tolerability. The IMP dose may be increased by increments of 2.5 mg/kg BID (5 mg/kg/day) no more rapidly than every 7 days, up to a maximum daily dosage of 20 mg/kg/day.

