**Part A:**

- The duration of study participation in Part A is approximately 26 weeks, which includes a 1- to 3-week screening period, 4-week baseline observation period, 14-week dose-optimization treatment period, 10-day taper period, and a safety follow-up period (4 weeks after end-of-taper visit).
- After the informed consent/assent form has been signed, participants will be screened to enter the study from Day -49 to Day -35 (Visit 1) and commence a 28-day baseline period beginning at Day -28 (Visit 2), before returning for a randomization visit and treatment initiation (Day 1 [Visit 3]).
- IMP administration during the 14-week treatment period will follow a flexible titration schedule to enable optimization of dosage.
- Visits 4 to 6 will be conducted as phone visits; Visit 7 will be completed in clinic, and Visit 8 will be completed in clinic or at home visit. Participants will then return to the study site for an end of treatment visit (Day 99 [Visit 9]). If a participant withdraws from the study prematurely (ie, before the end of treatment visit) an early withdrawal visit will be conducted, and a safety follow-up phone call will occur 4 weeks after their last dose of IMP. If a participant discontinues IMP prematurely, they should be encouraged to complete the end of treatment visit and the taper period and remain in the study. Participants not continuing to Part B of the study will return to the study site again at the end of the 10-day taper period (Day 110 [Visit 10]) and complete a phone safety visit at the end of the follow-up period (Day 138 [Visit 11]).
- Part B will be available to participants who complete Part A of the study and continue to meet all eligibility criteria and to participants for whom the investigator feels continued treatment in Part B represents a favorable risk-benefit assessment. Rollover into Part B should occur on the same day as Part A Day 99 (Visit 9).
- Unscheduled phone visits can occur at any time throughout Part A, as needed.

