**Table 1: Schedule of Activities: Part A**

Study Period	Screening	Baseline Period	14-Week Dose-Optimization Treatment Period						EOT or E/W	Taper Period	Safety FU	Notes
Visit Number	1	2	3	4	5	6	7	8	9	10	11	
Week	-	-	0	1	2	3	4	8	14	16	20	
Day	-49 to -35	-28	1	8	15	22	29	57	99	110	138	
Visit Window (days)	-	-	+3	±3	±3	±3	±3	±7	±7	+3	±7	
Visit Type	Clinic	Phone	Clinic	Phone	Phone	Phone	Clinic	Clinic*	Clinic	Clinic	Phone	
IMP Administration												
eDiary Training	X											
Seizure Classification Training		X										
IMP and dosing eDiary training			X									
Dosing in clinic			X						X			
At home dosing			X	X	X	X	X	X	X	X		
IMP dosing frequency			2.5 mg/kg BID	5 mg/kg BID	5 or 7.5 mg/kg BID	5, 7.5, or 10 mg/kg BID			Reduce by 10% per day over 10 days		Section 6.5	
eDiary Completion (Daily)	←————→										Section 8.1.4	
eDiary Review		X	X	X	X	X	X	X	X		Section 8.1.4	
IMP Dispensing			X				X	X	X		Section 8.11	
IMP Return							X	X	X	X		
IMP Accountability							X	X	X	X		
IMP Dosing eDiary Compliance				X	X	X	X	X	X	X		Section 6.4

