Participants will complete weekly scheduled phone visits at Day 8 (Visit 4), Day 15 (Visit 5), and Day 22 (Visit 6) and complete an in-clinic visit at Day 29 (Visit 7) and an in-clinic or home visit for review of symptoms and safety laboratory tests and to return/dispense IMP at Day 57 (Visit 8). Participants will then return to the study site for an end of treatment visit (Day 99 [Visit 9]). If a participant withdraws from the study prematurely (ie, before the end of treatment visit), an early withdrawal visit will be conducted, and a safety follow-up phone call will occur 4 weeks after their last dose of IMP. If a participant discontinues IMP prematurely, they should be encouraged to complete the end of treatment visit and the taper period and remain in the study.

Participants not continuing to Part B will return to the study site again at the end of the 10-day taper period (Day 110 [Visit 10]) and will complete a phone safety visit at the end of the follow-up period (Day 138 [Visit 11]).

Part B will be available to participants who complete Part A of the study and continue to meet all eligibility criteria and to participants for whom the investigator feels continued treatment in Part B represents a favorable risk-benefit assessment. Rollover into Part B should occur on the same day as Part A Day 99 (Visit 9).

Unscheduled phone visits can occur at any time throughout Part A, as needed.

AE, concomitant medication, and rescue medication eDiaries will be completed each day during the screening period, baseline observation period, treatment period, and taper period beginning at screening (Visit 1).

Seizure eDiaries will be completed each day during the screening period, baseline observation period, and treatment period beginning at screening (Visit 1).

IMP dosing eDiaries will be completed each day during the titration, treatment, and taper periods beginning at randomization (Visit 3).

Food eDiaries will be completed for approximately 24 hours prior to each visit where PK blood samples will be collected beginning approximately 24 hours prior to randomization (Visit 3).

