After Part B Week 14 (Visit 7), serum transaminases and total bilirubin levels should be evaluated within 1 month following changes in GWP42003-P dosage and in medications that are known to impact the liver.

- As much as possible, laboratory assessments should be done centrally via IQVIA Mobile Health Solutions (if done locally, laboratory results should be filed in source documents and any abnormal and clinically significant results should be recorded as AEs)

A safety follow-up visit (phone call) will be conducted 4 weeks after the end-of-taper visit. If a participant withdraws from the study prematurely (ie, before the end of treatment visit), an early withdrawal visit will be conducted, and a safety follow-up phone call will occur 4 weeks after their last dose of IMP. Participants who discontinue IMP prematurely should be encouraged to complete the end of treatment visit and taper period.

Unscheduled phone visits can occur at any time during Part B, as needed.

During Part B, eDiaries will be completed at least weekly. No food eDiary is required for Part B.

Schematics ([Figure 1](#) for Part A and [Figure 2](#) for Part B), presented in [Section 1.2](#), depicts the overall trial design. A detailed outline of procedures and activities is provided in the SoA

([Table 1](#) for Part A and [Table 2](#) for Part B). More detailed information on treatment and study procedures is provided in [Section 6](#) and [Section 8](#), respectively.

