### 7.1. Discontinuation of Study Intervention

Reasons for removal from IMP include any of the following:

- Participants may decline to continue receiving IMP or other protocol-required therapies or procedures at any time during the study.
  - Participants who choose to discontinue IMP or other protocol-required therapies or procedures should not be automatically removed from the study. Whenever safe and feasible, and in agreement with the sponsor, the participants should remain in the respective part of the study to ensure safety surveillance and collection of outcome data. Specifically, participants who discontinue IMP prematurely in Part A of the study will not be enrolled in Part B.
  - The investigator is to discuss with the participant the appropriate processes for discontinuation from IMP or other protocol-required therapies. The investigator must discuss with the participant the possibilities for continuation of activities described in the SoA ([Table 1](#) and [Table 2](#)) and must document this decision in the eCRF.
- Decision by investigator.
- Decision by sponsor.
- Withdrawal by participant/caregiver/legal representative.
- Lack of efficacy.
- Change in compliance with any inclusion/exclusion criterion that is clinically relevant and affects participant safety, as determined by the investigator (or designee).
- Protocol deviation that is considered to potentially compromise the safety of the participant.
- Noncompliance with IMP.
- Noncompliance with study assessments.
- Pregnancy.
- Liver Chemistry - Discontinuation of IMP for abnormal liver tests is required by the investigator when a participant meets one of the following conditions outlined or in

the presence of abnormal liver chemistries not meeting protocol-specified stopping rules if the investigator believes that it is in best interest of the participant.

- Serum ALT or AST  $> 3 \times \text{ULN}$  with the presence of fatigue, nausea, vomiting, right upper quadrant pain or tenderness, fever, rash, and/or eosinophilia ( $> 5\%$ ).
- ALT or AST  $> 8 \times \text{ULN}$ .
- ALT or AST  $> 5 \times \text{ULN}$  for  $> 2$  weeks.
- ALT or AST  $> 3 \times \text{ULN}$  **and** (TBL  $> 2 \times \text{ULN}$  **or** INR  $> 1.5$ ).
- Note: Refer to [Section 10.6](#) (Appendix 6) for information on follow up for clinically significant liver results.
- Any evidence of drug abuse or diversion.

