## 7.2. Participant Withdrawal from the Study

A participant may withdraw from the study at any time at his/her own request or may be withdrawn at any time at the discretion of the investigator or sponsor for safety, behavioral, or compliance reasons.

- The participant will be permanently discontinued both from the IMP and from the study at that time.
- If a participant is withdrawn from the study, the study monitor will be informed immediately. If there is a medical reason for withdrawal, the participant will be followed up by the investigator until satisfactory health has returned.
- All efforts must be made to complete and report the observations as thoroughly as possible up to the date of withdrawal.
- Participants withdrawing due to an AE should be followed up according to [Section 10.4.4](#). All information should be reported on the applicable eCRF pages (refer to [Section 8](#)). A safety follow-up visit should take place  $\pm 7$  days after last dose of IMP (refer to [Table 1](#) and [Table 2](#)). If withdrawing participants decline to give a reason for withdrawal of consent, the investigator must respect the participant's wishes.
- If the participant withdraws consent for disclosure of future information, the sponsor may retain and continue to use any data collected before such a withdrawal of consent.
- If a participant withdraws from the study, he/she may request destruction of any samples taken and not tested, and the investigator must document this in the site study records.

Reasons for removal of a participant from the study are:

- Decision by investigator.
- Decision by sponsor.
- Lack of efficacy.
- AE.
- Withdrawal by participant/caregiver/legal representative.
- Death.
- Lost to follow up.

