## 10.6. Appendix 6: Liver Safety: Actions and Follow-up Assessments

All investigational sites are required to submit to the sponsor PVD the laboratory results for any participant after randomization that meets the criteria for the selected laboratory parameters as follows:

- Serum ALT or AST  $> 3 \times \text{ULN}$  with the presence of fatigue, nausea, vomiting, right upper quadrant pain or tenderness, fever, rash, and/or eosinophilia ( $> 5\%$ ).
- ALT or AST  $> 8 \times \text{ULN}$ .
- ALT or AST  $> 5 \times \text{ULN}$  for  $> 2$  weeks.
- ALT or AST  $> 3 \times \text{ULN}$  **and** (TBL  $> 2 \times \text{ULN}$  **or** INR  $> 1.5$ ).

These reports must be sent to the sponsor PVD using the fax number or by e-mail for SAE reporting within 24 hours of becoming aware of the results. In addition, please send a copy of the participant's baseline laboratory results with all reports to the sponsor PVD.

Abnormal values in AST and/or ALT with or without concurrent abnormal elevations in TBL that meet the criteria outlined above are considered potential cases of drug-induced liver injury and will be considered as protocol-defined criteria for withdrawal and important medical events. The investigator will arrange as soon as possible (within 24 hours of notice of abnormal results) for repeat assessment of ALT, AST, TBL, INR, full blood count (and differential count), eosinophil counts, ALP, and GGT levels, creatine kinase levels, detailed history, and physical examination. Participants should be followed with frequent (every 48 to 72 hours) repeat clinical laboratory assessments and any other appropriate assessments until all abnormalities have normalized (in the investigator's opinion) or returned to the baseline state.

Elevations in ALT or AST  $> 3 \times \text{ULN}$  **or** TBL  $> 2 \times \text{ULN}$  alone are not considered potential cases of drug-induced liver injury, but will be followed as detailed above, within 72 hours' notice of abnormal results. If the participant is no longer at the investigational site, repeat assessments may be performed at a local laboratory and the results sent to the sponsor PVD.

Refer to [Section 7](#) for study withdrawal/discontinuation criteria.

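### The protocol gives inconsistent instructions on the 10-day taper after early IMP discontinuation, so it is unclear whether a required liver stop is tapered or immediate

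*Combined protocol and SAP*

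**What the plan says.** **Taper, mandatory form.** Section 1.1, under Study Intervention(s), Part B: "Participants not entering Part B or who discontinue IMP early will down-titrate over a period of 10 days". No reason for stopping is exempted.

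**Taper, voluntary form.** The Part A design text, in the synopsis and again in Section 4.1: "If a participant discontinues IMP prematurely, they should be encouraged to complete the end of treatment visit and the taper period", and to stay in the study. The Part B design text, in the same two places: "Participants who discontinue IMP prematurely should be encouraged to complete the end of treatment visit and taper period". Neither has an exception for safety stops.

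**Taper schedule.** Table 1 gives the step as "Reduce by 10% per day over 10 days"; Table 2 gives the same step for Part B.

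**Liver stop.** Section 7.1: "Discontinuation of IMP for abnormal liver tests is required by the investigator when a participant meets one of the following conditions". Four ALT/AST-based criteria follow. Nothing is said about timing or the taper.

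**Study withdrawal.** Section 7.2: "The participant will be permanently discontinued both from the IMP and from the study at that time". The taper is not mentioned.

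**Link between the two.** Appendix 6 (Section 10.6) repeats the four liver criteria and says that values meeting them are "considered potential cases of drug-induced liver injury and will be considered as protocol-defined criteria for withdrawal".

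Section 6.5, on dose modification, has no taper rule for early or safety-driven stops.

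**The concern.** A participant who meets a liver criterion must come off IMP. The protocol does not say whether dosing then ends at once or runs down over 10 days, and its statements point in different directions. One site could follow the synopsis sentence and continue at falling doses. Another could read Appendix 6 together with Section 7.2 and stop immediately. Each could cite the protocol.

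Participants are children from 1 year of age. Drug-induced liver injury is an adverse event of special interest (Section 10.4.3). Section 2.3 lists both hepatocellular injury and withdrawal of antiseizure medication among serious side effects, so neither reading is plainly the intended one. For the analysis, exposure after a liver stop would depend on how the site read the protocol.

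**Working it through.** **1. The statements side by side**

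| Place | Who it covers | Instruction on IMP | Exception for safety stops |
|---|---|---|---|
| 1.1, Study Intervention(s) | those who stop IMP early | 10-day taper, mandatory | none |
| 1.1 and 4.1, design text, Parts A and B | those who stop IMP early | taper encouraged | none |
| 7.1, liver criteria | those who meet a criterion | discontinuation required, no timing | taper not mentioned |
| 7.2 | those who leave the study | IMP ended when they leave | taper not mentioned |
| Appendix 6 | those who meet a 7.1 liver criterion | called a criterion for withdrawal | taper not mentioned |

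Three things follow.

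- The synopsis disagrees with itself and with Section 4.1: the taper is mandatory in one sentence and voluntary in the others.
- Section 7.1 alone does not contradict the taper. It requires discontinuation without saying how fast.
- A conflict over the liver stop arises when Appendix 6 is read with Section 7.2. If meeting a criterion means withdrawal from the study, Section 7.2 ends dosing then, while the synopsis sentence tapers anyone who discontinues IMP early.

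**2. What the literal taper would deliver**

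Inputs: a 10% daily reduction over 10 days (Tables 1 and 2), and maintenance doses d of 10, 15 or 20 mg/kg/day (Table 4). I take 10% as a share of the starting dose, because a 10% cut of the current dose would still leave 0.9^10 = 0.35 of it on day 10. The documents do not say whether the first taper day is already reduced, so both conventions are shown.

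- Convention A, first cut on taper day 1: 0.9 + 0.8 + … + 0.1 + 0.0 = 4.5 full-day equivalents over 9 dosing days.
- Convention B, first taper day at full dose: 1.0 + 0.9 + … + 0.1 = 5.5 full-day equivalents over 10 dosing days.

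Cumulative dose = d × full-day equivalents:

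| d (mg/kg/day) | A: d × 4.5 (mg/kg) | B: d × 5.5 (mg/kg) |
|---|---|---|
| 10 | 45 | 55 |
| 15 | 67.5 | 82.5 |
| 20 | 90 | 110 |

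Under Section 7.2 the figure is zero.

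**3. Check against the visit schedule**

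End of treatment to end of taper is 110 − 99 = 11 days in Part A and 348 − 337 = 11 days in Part B. Both fit a 10-day taper.

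**The case against.** The strongest reply is that the mandatory wording occurs once, in a summary, and that the rest of the protocol can be read coherently. The design text in Sections 1.1 and 4.1 separates two routes. Participants who leave the study have an early withdrawal visit and a call 4 weeks after the last dose, with no taper mentioned. Participants who stop IMP are encouraged to stay and taper. Section 8.1.4 treats the end of taper and the early withdrawal visit as alternative end points for the eDiary. On that reading Section 7.2 and the taper concern different people, and Table 1's column order does not show that withdrawers taper. This stands for ordinary study withdrawal. It does not settle the liver stop, because Section 7.1 treats the criteria as a reason to stop IMP while Appendix 6 calls them grounds for withdrawal.

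Safeguards also exist. Section 8 sends immediate safety concerns to the sponsor, Section 6.5 allows dose decreases for tolerability at any time, and Appendix 6 requires repeat testing within 24 hours and then laboratory tests every 48 to 72 hours. These make unsupervised continued dosing less likely, but none says whether the taper applies. The condition in Section 7.1 about safety and feasibility concerns staying in the study, not tapering. The printed dosing schedule (Section 6.2) and the pharmacy manual are not available here, so divergence between sites is an inference. Neither could remove a conflict inside the protocol.

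A reader might also infer that the last-dose date, and so the timing of follow-up, becomes undefined. The documents do not support that. Section 6.4 requires IMP stop dates and dose adjustments to be recorded. The date moves by 9 to 10 days between the readings because dosing differs, and it can be observed under either.

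**Conclusion.** The inconsistency is real and bears on participant safety. The taper after early discontinuation is mandatory in one synopsis sentence and voluntary elsewhere, and no text says whether a required liver stop is tapered. The literal readings differ by 9 to 10 dosing days at a falling dose, equal to 4.5 to 5.5 full-day doses: 45 to 55 mg/kg from 10 mg/kg/day, and 90 to 110 mg/kg from 20 mg/kg/day. In Part A this is active drug only for participants randomized to GWP42003-P.

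A reader might go further and infer that the protocol orders every participant with a liver stop to remain on drug, or that Section 7.1 itself forbids the taper. The documents support neither. The mandatory sentence stands alone against several voluntary ones, and Section 7.1 is silent on timing. For the liver stop this is an ambiguity that becomes a contradiction only through Appendix 6 and Section 7.2.

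The size rests on a linear taper from a maintenance dose of 10 to 20 mg/kg/day. The documents give no basis for estimating how many participants would be affected.

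**What to change.** Reconcile the treatment and design text in Section 1.1, Section 4.1 (Parts A and B), the taper entries in Tables 1 and 2, Sections 7.1 and 7.2, and Appendix 6:

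- State in one place, for each reason listed in Sections 7.1 and 7.2, whether the 10-day taper applies.
- Replace the unqualified synopsis sentence with a reference to that place, and do the same in Section 4.1.
- Make Appendix 6 say whether meeting a liver criterion means stopping IMP, leaving the study, or both.
- Bring the printed dosing schedule and pharmacy manual into line.

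Which rule applies in each case is a decision for the sponsor's medical team. The cost is a short wording amendment and a note to sites, with no added visits or procedures.

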### **Assessments**

The following assessments will be performed: informed consent/assent, eligibility check, medical history, epilepsy gene panel, demographics, physical examination, body weight, height, ECG, vital signs, electroencephalogram (if required) eligibility check, prior and concomitant medications recorded, electronic diary (eDiary) training, eDiary completion, questionnaires (C-SSRS, CGIC, PGIC, CGIC in Seizure Duration, [REDACTED] [REDACTED] Treatment [REDACTED]

Credibility/Expectancy Questionnaire and Parent Version, [REDACTED]

[REDACTED], menstruation questions, tanner staging, and AE monitoring.

Clinical laboratory tests including biochemistry, coagulation, hematology, urinalysis, pharmacokinetics, and pregnancy test will also be performed.

